
2.1 Objectives & Hypotheses
 
2.1 List the objectives.
 
Primary Objectives
 
 • To estimate the incidence of postoperative residual weakness (train-of-four ratio < 0.9) in patients receiving sugammadex after undergoing liver transplantation with quantitative monitoring 
Secondary Objectives
 
 • To estimate the proportion of patients that never require admission to the intensive care unit after receiving 'fast track' anesthesia • To estimate the mean hospital length of stay for patients receiving 'fast track' anesthesia and compare this to national averages • To estimate the frequency of postoperative pulmonary complications in patients receiving sugammadex as part of 'fast track' anesthesia 
2.1.1 List the clinical hypotheses.
 
Primary Study Endpoints
 
The primary endpoint of the study is the incidence of postoperative residual weakness in the recovery room following 'fast track anesthesia' during liver transplantation in which patients receive sugammadex and are monitored with quantitative monitoring. We believe the combination of sugammadex and quantitative monitoring represents best practice and will result in a low incidence (<5%) of residual weakness in this high risk group.
 
Secondary Study Endpoints
 
The secondary endpoints include whether a patient requires ICU admission following liver transplantation. We hypothesize that this number is low (<5%). Another secondary endpoint is hospital length of stay. We hypothesize this will be significantly less than the national average (10 days). Finally, the third endpoint is the occurrence of postoperative pulmonary complications defined as pneumonia, and respiratory failure in patients receiving 'fast track' anesthesia. We hypothesize that such complications occur rarely (<5%).
	
2.1 List the objectives.
 
Primary Objectives
 
 • To estimate the incidence of postoperative residual weakness (train-of-four ratio < 0.9) in patients receiving sugammadex after undergoing liver transplantation with quantitative monitoring 
Secondary Objectives
 
 • To estimate the proportion of patients that never require admission to the intensive care unit after receiving 'fast track' anesthesia • To estimate the mean hospital length of stay for patients receiving 'fast track' anesthesia and compare this to national averages • To estimate the frequency of postoperative pulmonary complications in patients receiving sugammadex as part of 'fast track' anesthesia 
2.1.1 List the clinical hypotheses.
 
Primary Study Endpoints
 
The primary endpoint of the study is the incidence of postoperative residual weakness in the recovery room following 'fast track anesthesia' during liver transplantation in which patients receive sugammadex and are monitored with quantitative monitoring. We believe the combination of sugammadex and quantitative monitoring represents best practice and will result in a low incidence (<5%) of residual weakness in this high risk group.
 
Secondary Study Endpoints
 
The secondary endpoints include whether a patient requires ICU admission following liver transplantation. We hypothesize that this number is low (<5%). Another secondary endpoint is hospital length of stay. We hypothesize this will be significantly less than the national average (10 days). Finally, the third endpoint is the occurrence of postoperative pulmonary complications defined as pneumonia, and respiratory failure in patients receiving 'fast track' anesthesia. We hypothesize that such complications occur rarely (<5%).


2.2 Background & Rationale, Significance of Selected Topic & Preliminary Data
	
Neuromuscular blocking agents (NMAs) are a class of medications routinely used during anesthesia to facilitate endotracheal intubation (1) and improve conditions for optimal surgery (2). Routine reversal of neuromuscular blockade is very common in order to return patients' spontaneous breathing and prevent residual blockade and all the associated complications (3, 4). Sugammadex, a γ-cyclodextrin, is a unique neuromuscular reversal drug first reported by Anton Bom. It is the first in a new class of selective relaxant binding agents, and it was designed to rapidly reverse rocuronium-induced neuromuscular block (5, 6). Sugammadex-rocuronium binding reduces the amount of free muscle relaxant in the plasma, reducing the level of free NMA at the neuromuscular junction (7). The dose of sugammadex depends on the level of blockade. While a peripheral nerve stimulator can provide some information regarding the level of blockade, quantitative neuromuscular monitoring is the only method to confirm adequate recovery prior to extubating the trachea (8). Empiric administration of sugammadex without proper monitoring reduces the incidence of postoperative residual weakness, however, this practice does not eliminate residual weakness (9). Optimal neuromuscular blockade management incorporates sugammadex and quantitative monitoring to minimize the risks associated with postoperative residual weakness.
 
Mayo Clinic in Jacksonville, Florida is one of the busiest liver transplantation centers in the world and has

been a pioneer in establishing ‘fast track’ anesthesia in which these patients emerge from anesthesia in the operating room, spend time in the recovery room, and are then transferred to their hospital room while bypassing the intensive care unit (11). This pioneering feature of our clinical practice allows for unique research opportunities. Last year Mayo Clinic Florida completed over 150 liver transplant patients with approximately 60% of these patients being ‘fast tracked’. Like other enhanced recovery pathways, optimal neuromuscular blockade management with quantitative monitoring and antagonism with sugammadex is a cornerstone of ‘fast track’ anesthesia for liver transplantation at our institution. Assessing level of neuromuscular blockade during these cases is typically achieved with a peripheral nerve stimulator and/or quantitative monitoring.

The purpose of this study is to determine the incidence of postoperative residual weakness (a train-of-four ratio < 0.9) in patients getting ‘fast track anesthesia’ following liver transplantation. Our clinical practice routinely utilizes sugammadex in this patient population and we have anecdotally observed excellent outcomes. We hypothesize that the incidence of postoperative residual weakness with sugammadex and quantitative monitoring is low (<5%) and that patients receiving fast track anesthesia have shorter hospital length of stays than the national average (12). Additionally, postoperative pulmonary complications (PPC) can occur from residual weakness. We will utilize previous definitions of PPCs (13). Specifically, postoperative pneumonia within 30 days or respiratory failure that requires unplanned non-invasive mechanical ventilation (such as bilevel positive airway pressure ventilation) or need for reintubation due to respiratory distress will be documented.

This unblinded, single center, prospective, randomized, observational study will involve 30 patients undergoing liver transplantation that receive ‘fast track anesthesia’.

Inclusion Criteria

- Age > or = 18 years old
- Patients willing to participate and provide an informed consent
- Patients undergoing primary liver transplantation

Exclusion Criteria

- Patients with unilateral disorders, such as stroke, carpal tunnel syndrome, broken wrist with nerve damage, Dupuytren contracture, or any similar wrist injury.
- Patients with systemic neuromuscular diseases such as myasthenia gravis
- Patients with a known history of cerebrovascular accident (CVA)
- Patients undergoing repeat liver transplantation or concomitant pancreas/kidney transplantation at the time of liver transplantation
- Patients admitted to the intensive care unit prior to liver transplantation.

Subject Recruitment, Enrollment and Screening

On an annual basis there are around 150 liver transplantsations performed at Mayo Clinic in Florida that require a pulmonary artery catheter and thus no difficulties in accrual based on historical volumes are anticipated. We expect that approximately 3 participants per week will be completed for this study. The initial accrual period will last at least 4 months. Patients will be provided with a Research Participant Consent and Privacy Authorization Form describing the study protocol, inclusion and exclusion criteria, as well as risks and benefits of participation.

Method of Assigning Subjects to Study Groups

This is an open-label pilot investigation and all study participants are assigned to receive their routine standard of care intraoperatively. The randomization involves whether patients are monitored with a

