- The patient's electronic medical record will be reviewed for up to 30 days postoperatively. Patient characteristics such as age, gender, albumin level, type of surgery, and baseline glomerular filtration rate will be recorded.

Schedule of Events		
Study Activity	Visit 1	Visit 2
TetraGraph/Peripheral Nerve Stimulator		X
Sugammadex		X
Informed consent	X	
Review of Medical Record	X	X
Adverse event evaluation		X

| **2.7 Study Duration** | Subject participation will be 3-6 hours, depending on duration of surgery. The entire study will be completed within 2 years based on the total number of eligible patients. | |
| **2.8 Statistical Analysis and Sample Size Justification** | This is an open-label investigation. Masking and blinding procedures are not applicable. **Sample Size Determination** Assuming the incidence of postoperative weakness incidence with sugammadex without quantitative monitoring is 46% (9) and the incidence of weakness with sugammadex and a quantitative monitor is 5% (11), 28 patients would be required to be powered (80% power, $p<0.05$) to show evidence of a reduction in residual weakness with the use of quantitative monitoring to below 46%. However, we will consent up to 100 patients to account for possible dropouts and missing data to meet target accrual of 30 patients. **Statistical Methods** Continuous variables will be summarized as mean (standard deviation) or median (range) while categorical variables will be reported as frequency (percentage). For the primary aim, we will calculate the proportion of patients who have postoperative weakness, expressed as a percentage; we will perform a one-sample binomial test of the null hypothesis that the true proportion is 46%, and we will calculate an exact binomial 95% confidence interval (CI) for the true proportion of postoperative weakness for patients who are fast tracked. For the first secondary aim, we will similarly calculate the proportion of patients who go to the ICU, expressed as a percentage along with a 95% CI for the true proportion. For the second secondary aim we will calculate the sample mean length of stay of the patients in the study along with a 95% CI – due to the skewness of the distribution of length of stay we will construct a bootstrap-based CI. For the third secondary aim, we will calculate the proportion of patients who have postoperative | |

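### Section 2.8 offers evidence of a reduction with quantitative monitoring, but a wholly monitored cohort can only be compared with an external 46%; separately, the <5% hypothesis has no matching test

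*Combined protocol and SAP*

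**What the plan says.** - **Objective (2.1).** The primary objective is one of estimation: "To estimate the incidence of postoperative residual weakness (train-of-four ratio < 0.9) in patients receiving sugammadex".
- **Hypothesis (2.1.1).** The investigators believe that sugammadex plus quantitative monitoring "represents best practice and will result in a low incidence (<5%) of residual weakness in this high risk group". The statement of purpose that follows the background repeats the <5% figure as a hypothesis.
- **Sample size (2.8, Sample Size Determination).** The plan assumes 46% without quantitative monitoring and 5% with it, both from cited references. It arrives at 28 patients for 80% power at p<0.05, to "show evidence of a reduction in residual weakness with the use of quantitative monitoring to below 46" per cent. The accrual target is 30.
- **Analysis (2.8, Statistical Methods).** For the primary aim, after the observed proportion, "we will perform a one-sample binomial test of the null hypothesis that the true proportion is 46" per cent, and "we will calculate an exact binomial 95% confidence interval (CI) for the true proportion of postoperative weakness" in fast-tracked patients.
- **Allocation (2.3 and 2.6).** "This is an open-label pilot investigation and all study participants are assigned to receive their routine standard of care intraoperatively". Randomisation is to TetraGraph on the dominant or the nondominant hand. Visit 2 says the device is placed before induction and that its values guide care.

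**The concern.** The sample-size sentence credits the study with evidence about the use of monitoring. Such evidence needs patients managed without it, and there are none. If the wording passes into the abstract or manuscript, a very small p-value against 46% could be presented as a benefit of monitoring. Yet any gap between this cohort and the cited study may also reflect who was selected, how they were anaesthetised and reversed, and how weakness was measured.

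The second issue is smaller. The stated hypothesis is <5%, but the only formal primary test and the sample size concern 46%. The plan does not say what 30 patients can establish about 5%, so a reader may take an estimate such as 1/30 (3.3%) as confirmation.

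**Working it through.** **1. The plan's own figure.** Inputs from 2.8: null rate 0.46, planning rate 0.05, 80% power, alpha 0.05 (sidedness not stated).

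- Under the planned one-sample exact test, power first reaches 80% at n = 9, one- or two-sided. The test rejects at 0 or 1 event, with power 0.95^9 + 9 × 0.05 × 0.95^8 = 0.630 + 0.299 = 92.9%.
- At n = 28 the two-sided test rejects at 7 events or fewer, and power is 99.995%, not 80%. The stated 28 is therefore not reproduced.
- An unpooled two-group formula gives (1.960 + 0.842)² × (0.46 × 0.54 + 0.05 × 0.95) / 0.41² = 13.8, so 14 per arm and 28 in total. This match does not prove how 28 was obtained, and the point below does not rest on it.

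**2. What the comparison contains.**

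| Needed for a statement about monitoring | What the plan provides |
|---|---|
| Patients managed without quantitative monitoring | None; all carry TetraGraph and its values guide care |
| Allocation to monitored or unmonitored | Allocation to dominant or nondominant hand only |
| A concurrent comparison rate | A fixed 46% from a cited study |
| Comparable patients | Only those declared fast-track candidates after recirculation; the others are screen failures |

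The Schedule of Events has a combined row for TetraGraph and peripheral nerve stimulator, but no participant is assigned to the stimulator alone. Comparing the two hands would say nothing about monitored against unmonitored care.

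**3. What the test against 46% can show at n = 30.** It rejects low at 0 to 8 events: 8/30 gives two-sided p = 0.043 and 9/30 gives 0.099. One-sided at 0.05 the set is the same (0.024 and 0.056). The chance of rejection is above 0.999 at a true 5% and still 0.87 at an assumed true 20%. Rejection means that the cohort's incidence is below 46%, and nothing more specific.

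**4. What the exact interval can show about 5%.** With no events in n patients, the two-sided exact 95% upper limit is 1 − 0.025^(1/n).

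- 0/30: 1 − 0.025^(1/30) = 11.6%. A one-sided 95% limit, 1 − 0.05^(1/30), is 9.5%.
- 1/30 (3.3%): 0.1% to 17.2%.
- 2/30 (6.7%): 0.8% to 22.1%.
- For scale, n = 71 with no events gives 5.06% and n = 72 gives 4.99%.

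At a true 5%, 0/30 occurs with probability 0.95^30 = 21.5% and 1/30 with probability 30 × 0.05 × 0.95^29 = 33.9%. A point estimate below 5% therefore occurs 55.4% of the time, but never with an upper limit below 5%.

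**The case against.** The strongest reply is that the study does not set out to confirm 5%. Its objective is to estimate, it is labelled a pilot, and the <5% figure is introduced as a belief with no test, power claim or decision rule attached. The planned exact interval will show the imprecision whatever the result. Requiring an upper limit below 5% is a criterion the protocol never sets. This largely stands: it reduces the second issue to an unstated precision limit.

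On the first issue, the reply is that the test sentence in Statistical Methods is neutral, that 46% is openly attributed to a reference, and that the contested wording occurs once, in the sample-size rationale. All of that is true, and it limits the error to that sentence. It does not remove it, because that sentence states what the sample is powered to show, and the design cannot show it.

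A reader might go further and infer that the plan treats rejecting 46% as support for <5%, or that its primary analysis can contradict itself. At 5 to 8 events in 30 the test is significant while the exact interval lies wholly above 5% (5/30: p = 0.0014, interval 5.6% to 34.7%; 8/30: interval 12.3% to 45.9%). The documents do not support that inference. They nowhere say that rejecting 46% supports <5%, and the two results are compatible: the rate would lie between 5% and 46%. At the planning rate of 5% the combination has probability 1.6%. It is 17%, 45% and 62% at true rates of 10%, 15% and 20%, but those rates are assumptions, and under them an interval above 5% is the right answer.

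**Conclusion.** The sample-size sentence in 2.8 is wrong as written. With every participant monitored and only the hand randomised, the one-sample test can show that this fast-track cohort's incidence is below an external 46%. It cannot show a reduction with the use of monitoring. This follows from the design and depends on no assumed rate.

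The <5% hypothesis is a secondary gap. Neither the test nor the sample size addresses it. If confirmation means the planned exact 95% interval lying below 5%, no result at n = 30 achieves it, the best upper limit being 11.6%. That criterion is an assumption of this review; a point estimate below 5% remains possible with 0 or 1 event.

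A reader might also conclude that the planned test is invalid or that the study is too small. Neither follows. The test is valid for the null it states, and 30 patients can support an estimate reported with its interval.

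**What to change.** Keep n = 30 and every planned analysis.

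1. In 2.8, Sample Size Determination, replace the phrase about a reduction with monitoring by *an incidence in this cohort below the external benchmark of 46%*, and state that no conclusion about the effect of monitoring will be drawn from the test.
2. In 2.1.1 and the statement of purpose, restate <5% as an expectation to be described by the estimate and its exact 95% interval, noting that the best attainable upper limit at n = 30 is 11.6% (0/30).

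Naming the exact interval as the primary result would suit the estimation objective but is optional.

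The cost is editing in three places, with no extra patients, data or analyses. The only downside is that the stated conclusions become less favourable. These edits do not settle the derivation of 28, which is a separate matter.

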2.3 Study Design

quantitative monitor (TetraGraph) on their dominant or nondominant hand.

The randomization will be performed utilizing REDCap and assigned anesthesia clinical care team will be informed of patients' assignment to guide them with the selection of the appropriate monitoring option.

Data Handling and Record Keeping

Confidentiality

Information about study subjects will be kept confidential and managed according to the requirements of the Health Insurance Portability and Accountability Act of 1996 (HIPAA). Those regulations require a signed subject authorization informing the subject of the following:

- What protected health information (PHI) will be collected from subjects in this study
- Who will have access to that information and why
- Who will use or disclose that information
- The rights of a research subject to revoke their authorization for use of their PHI.

In the event that a subject revokes authorization to collect or use PHI, the investigator, by regulation, retains the ability to use all information collected prior to the revocation of subject authorization. For subjects that have revoked authorization to collect or use PHI, attempts should be made to obtain permission to collect at least vital status (long term survival status that the subject is alive) at the end of their scheduled study period.

Source Documents

Source data is all information, original records of clinical findings, observations, or other activities in a clinical trial necessary for the reconstruction and evaluation of the trial. Source data are contained in source documents. Examples of these original documents, and data records include: hospital records and any forms completed specifically for this study.

Case Report Forms

All data necessary for this study will be obtained from EHR or at the time devices are being used and recorded on the electronic Case Report Forms (CRFs) created in REDCap. All missing data will be explained.

Data Management

Study data to be collected and managed using EHR and study-generated source documents and transcribed into electronic CRFs in REDCap, electronic data capture software, hosted by CTSA at Mayo Clinic. REDCap (Research Electronic Data Capture) is a secure, web-based application designed to support data capture for research studies, providing 1) an intuitive interface for validated data entry; 2) audit trails for tracking data manipulation and export procedures; 3) automated export procedures for seamless data downloads to common statistical packages; and 4) procedures for importing data from external sources.

Data Processing

All study data will be stored and analyzed at Mayo Clinic in Florida using the REDCap electronic data capture tool.

Data Security and Confidentiality

All source documents including clinical findings, observations or other activities will be stored in a REDCap database that will be designed by an Investigator. Access to the REDCap database will be limited to the Principal Investigator, Investigators, Study Team members, and Statistician.

Data Quality Assurance

Once the study is completed the Principal Investigator will randomly select 3 participants and compare the data documented in the EHR with what is entered into the REDCap database. If there is any discrepancy, the Principal Investigator and/or Investigators will cross-reference all 30 patients to ensure accuracy.

Data Clarification Process

For any data query the Principal Investigator and Investigators will meet to clarify the data queried and make corrections based on consensus.

Records Retention

The sponsor-investigator will maintain records and essential documents related to the conduct of the study. These will include subject case histories and regulatory documents. Each site's Principal Investigator will maintain regulatory and essential study documents to ensure compliance with local and federal policies/guidelines.

The sponsor-investigator will retain the specified records and reports:

1. As outlined in the Mayo Clinic Research Policy Manual –“Retention of and Access to Research Data Policy” [REDACTED]

Study Monitoring, Auditing, and Inspecting

Study Monitoring Plan

The investigator will allocate adequate time for such monitoring activities. The Investigator will also ensure that the compliance or quality assurance reviewer is given access to all the study-related documents.

Auditing and Inspecting

The investigator will permit study-related monitoring, audits, and inspections by the IRB, the sponsor, and government regulatory agencies, of all study related documents (e.g. source documents, regulatory documents, data collection instruments, study data etc.).

[figure not shown]
Participation as an investigator in this study implies acceptance of potential inspection by government regulatory authorities and applicable compliance offices.

Ethical Considerations

This study is to be conducted according to United States and International government regulations and

	
Institutional research policies and procedures.
 
This protocol and any amendments will be submitted to a properly constituted local Institutional Review Board (IRB), in agreement with local legal prescriptions, for formal approval of the study. The decision of the IRB concerning the conduct of the study will be made in writing to the sponsor-investigator before commencement of this study.
 
All subjects for this study will be provided a consent form describing this study and providing sufficient information for subjects to make an informed decision about their participation in this study. This consent form will be submitted with the protocol for review and approval by the IRB for the study. The formal consent of a subject, using the Approved IRB consent form, must be obtained before that subject undergoes any study procedure. The consent form must be signed by the subject and the individual obtaining the informed consent.

2.4 Diversity & Inclusion	We plan to enroll the 30 patients regardless of race or gender. Every patient listed on the liver transplant list will be approached and invited to participate in this study.

